10.0 Data Management

All data will be safeguarded for confidentiality. Families will be assigned an unique identifier (UID) immediately following enrollment into the study. All sources of data will only have reference to the UID number. A file will also be created that links participants to their UID number. This file, consent and assent documents, screening documents, and de-identified data will all be kept in separate, locked file cabinets in the offices of the RAs at the Medical University of South Carolina in the Division of Global and Community Health (MUSC-GCH). Only study research personnel will have access to data that links research data to participant identifiers during the course of the trial.

Data Analysis Strategy

We will utilize a Pearson correlation coefficient (range -1 to 1) to determine the degree of correlation between components of DWN-FIT and engagement and adherence. Each measure will be quantized into a numerical value that can be used to generate the correlation coefficient. To compare the effect of SS on treatment outcomes we will use an independent two-sample t-test ($\alpha = 0.05$) to determine statistical differences between measures such as step count, PA, SM, etc. with respect to treatment condition.

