9.0 Study Design / Methods

Study participation will last 3 months. Families who consent to participate will be instructed to download the DWN app and complete a demographics survey. The research assistant will schedule the first session with the CHW and mail the weight scale, yoga mat, resistance bands, and Fitbit Inspire 3s to the family. Families will be randomly assigned to one of two intervention groups: the DWN-FIT or the DWN-FIT_Social Support (SS) group. CHWs will meet with families once a week for 3 months via video chat interface on the DWN-FIT app. The sessions will last approximately 45-minutes to 1 hour and will include: 1) review of SM goals; 2) review of PA steps and calories burned; 3) goal setting based on assessments and learning modules; and 4) review of CBST learning modules using evidence-based steps for skill acquisition (discussion of rationale, modeling of skill, caregiver and AAAO behavioral rehearsal of skill, feedback), and caregiver and AAAO develop implementation plans for between session skills practice.

We will also conduct a focus group with the participants after W12 of the study. These 17 focus groups (16 with participants and support person and 1 with all CHWs) will be guided by the responses to the needs analysis and usability evaluation; however, the questions will be open-ended to encourage discussions to obtain a fuller understanding of their personal experiences using the DWN. We will subsequently transcribe the audio recordings and group the data based on the discussion questions. Then, we will use either an inductive thematic analysis or a bottom-up technique to identify themes or recurring patterns in the responses. Caregivers, AAAOs, Supporters, and CHWs will be compensated \$195.55 for participating in a focus group.

Aim 1: Feasibility Testing. Evaluate the DWN-FIT intervention (delivered by 2 CHWs) with 16 families (AAAO and caregiver, overweight or obese) undergoing treatment for adolescent obesity to determine the degree to which the components of the digital intervention are correlated with adolescent-caregiver engagement in healthy behaviors and adherence to the prescribed treatment. Additionally, we will determine the degree to which SS, as an additional element of DWN-FIT, enhances engagement and retention of families within treatment.

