Methods: This aim follows two conditions (DWN-FIT vs DWN-FIT_Social Support [SS]) x 4 time (T0: baseline, T1: 1-month follow-up, T2: 2-month follow-up, and T3: 3-month end of treatment), with random assignment of 16 families (caregivers/AAAO) to one of the two treatment conditions. The proposed 3-month treatment period is too short to assess the feasibility of this digital treatment with respect to weight loss measurements (secondary outcomes), so instead we will assess feasibility of this approach based on the development of healthy behaviors (primary outcomes) that have been shown to lead to sustainable weight loss over time. Primary outcomes will be measured after each session (weekly) through the data recorded by the DWN app. These primary measures consist of the following measurements via the DWN app: step count, PA and PA video views, frequency and consistency of nutrition SM, messaging read and response rates, frequency and consistency of CBST education participation, telehealth session attendance, and CM rewards. In both treatment conditions, we will determine correlation between these measures and our measures of engagement and adherence. We will also determine the effect of semi-automated SS on each of the measures by comparing outcomes from each treatment group (DWN-FIT vs DWN-FIT_SS). Caregiver and AAAO percent

overweight and body-mass index (BMI) will serve as secondary outcome measures and will be collected each week via a provided digital scale. These secondary outcomes will be used to build preliminary data for a future full time-course (6-month or greater) randomized clinical trial (RCT).

Measures: We will measure **engagement** through the delivery of the 9-item Patient Health Engagement (PHE)⁴⁸ survey. The PHE is used to determine the degree to which patients are engaged in their own health and describes the patient's ability to manage their own health. PHE has been validated in other work, but a sample size large enough to meet this threshold is outside the scope of this study. The PHE outcomes gathered here will be used as preliminary data for future studies. The PHE survey will be taken via the DWN app at each time point, T0-T3. We will measure **adherence** through comparing the prescribed tasks against the task completed, raw counts (video views, SM entries, PA participation), by each set of participants. We will explore how SS is correlated with adherence to the prescribed treatment.

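### The social-support effect is tested without baseline adjustment although engagement and BMI have baseline values; the test is valid but gives up precision for those outcomes

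*Protocol*

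**What the plan says.** The design is two conditions by four time points, T0 to T3, "with random assignment of 16 families (caregivers/AAAO) to one of the two treatment conditions" (section 9.0). Section 5.0 puts 8 families in the social-support (SS) arm, which leaves 8 in the other.

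The only between-arm method is in section 10.0: "To compare the effect of SS on treatment outcomes we will use an independent two-sample t-test", at alpha 0.05, applied to "measures such as step count, PA, SM, etc. with respect to treatment condition". No covariate is named. The text does not say whether final values, averages or changes are compared.

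Baseline values exist for some outcomes (section 9.0):
- **Engagement.** Aim 1 states that "we will determine the degree to which SS, as an additional element of DWN-FIT, enhances engagement and retention of families within treatment". Engagement is defined as the PHE score, and "The PHE survey will be taken via the DWN app at each time point, T0-T3".
- **Weight.** Caregiver and adolescent percent "overweight and body-mass index (BMI) will serve as secondary outcome measures and will be collected each week via a provided digital scale", intended as preliminary data for a later randomised trial. The schedule table shows BMI at week 0.

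**The concern.** The protocol asks whether SS improves engagement and measures engagement before treatment, but the stated test does not mention that measurement. The same applies to BMI and percent overweight if they are compared between arms.

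With 8 families per arm, randomisation often leaves the arms visibly different at the start. If final values are compared, such a gap shifts the estimated effect in that dataset by roughly the correlation times the gap. For example, a 0.5 SD gap at an assumed correlation of 0.7 shifts it by 0.7 × 0.5 = 0.35 SD. What is at stake is the usefulness of a single 16-family dataset for planning the next trial, when information already collected could sharpen it.

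**Working it through.** The protocol gives no power, effect size, SD or interval width, so there is no figure of its own to reproduce.

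**Inputs.** From the protocol: 8 families per arm, N = 16 (sections 5.0 and 9.0), and alpha 0.05, taken as two-sided because sidedness is not stated. Assumed: the family as unit, all 16 families contributing data, and a baseline-outcome correlation R between 0 and 0.9. Results are in SD units of the outcome.

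**Chance imbalance.** The SE of a baseline difference is √(2/8) = 0.5 SD. The probability of a gap above 0.5 SD in either direction is 2 × (1 − Φ(0.5/0.5)) = 2 × (1 − Φ(1)) = 0.317.

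**Unadjusted test.** On 14 degrees of freedom the 95% half-width is 2.145 × 0.5 = 1.07 SD. Power is 46% for a true difference of 1.0 SD, and 80% power needs 1.51 SD.

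**Adjusted for one baseline covariate.** The width relative to the unadjusted final-value test is √[(1 − R²) × (1 + 1/(16 − 1 − 3))] × t(0.975, 13)/t(0.975, 14) = √[(1 − R²) × 1.0833] × 1.0073. For R = 0.7 this is √(0.51 × 1.0833) × 1.0073 = 0.749.

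**Change-score t-test.** The relative width is √[2(1 − R)].

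| Assumed R | Adjusted / unadjusted width | Adjusted half-width (SD) | Change-score / unadjusted width |
|---|---|---|---|
| 0 | 1.048 | 1.12 | 1.414 |
| 0.3 | 1.000 | 1.07 | 1.183 |
| 0.5 | 0.908 | 0.97 | 1.000 |
| 0.7 | 0.749 | 0.80 | 0.775 |
| 0.9 | 0.457 | 0.49 | 0.447 |

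Adjustment breaks even at R = √[1 − 1/(1.0833 × 1.0073²)] = 0.30.

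**Check by simulation** (40,000 trials at each R). The simulated width ratios were 1.04, 1.00, 0.90, 0.75 and 0.46, in line with the formula. The unadjusted test kept a type I error of 0.050 to 0.052 with a mean estimate of about zero at every R.

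**Which recorded values precede treatment.**
- PHE: the text says T0, but the schedule table, as it reads, has the first tick at week 1.
- Body fat: the first tick is at week 1.
- BMI: a week 0 value exists, but it appears to rest on self-reported height and weight confirmed by phone (section 7.0), whereas follow-up uses the mailed scale (section 9.0).
- Step count: Fitbit wear begins in W1 (section 3.0), although the table ticks steps at week 0.

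This matters because education content starts in W1 and supporters are prompted one day after each module release (section 3.0). A week 1 value may therefore already carry some SS effect.

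**The case against.** **The outcomes named for the t-test are behaviours.** The sentence in section 10.0 lists step count, physical activity and self-monitoring. In section 9.0, "We will also determine the effect of semi-automated SS on each of the measures by comparing outcomes from each treatment group" follows the list of app-recorded measures. That PHE and weight are also tested this way is read from the broader wording on treatment outcomes and, for PHE, from Aim 1. This stands, and it limits the point: for the named behaviours a true pre-intervention value is not clearly collected, so the interval cannot be called wider than it need be.

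**A reader might infer that chance imbalance biases or invalidates the comparison.** It does not. Over repeated randomisations the imbalance is random error already reflected in the standard error, as the simulation shows.

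**A reader might infer that the intervals for weight are several times too wide.** That needs a correlation near 0.95 (ratio 0.327), which the protocol does not give. Self-reported baseline weight against a scale reading later makes so high a value less certain.

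**A reader might infer that the protocol discards baseline altogether.** It does not say so. A t-test on change from baseline is still a two-sample t-test and is not excluded. At 0.7 it gives most of the gain (0.775 against 0.749), and at 0.9 it does as well as adjustment. At 0.5 it gives none, and below 0.5 it is worse than comparing final values. The choice between final values and changes may also be settled in an SAP that is not available here, so that omission is not itself held against the protocol.

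**No confidence intervals are promised.** True, but the same precision determines the power of the t-test that is promised.

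**Conclusion.** The point holds as one of efficiency, limited to outcomes with their own pre-intervention value: PHE, and BMI or percent overweight. Section 10.0 states an unadjusted test as the only between-arm method while those baselines are collected. The gain over a final-value t-test is about 9%, 25% and 54% of the interval width at correlations of 0.5, 0.7 and 0.9, and nothing at about 0.3 or below. The gain over a change-score test is appreciable only at moderate or low correlations.

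These sizes rest on assumed correlations, complete data from 16 families and the family as unit. Even at 0.7 the half-width would be about 0.80 SD, so the pilot stays imprecise whichever analysis is used. The protocol itself regards three months as too short to judge feasibility on weight loss, so no promised conclusion turns on this. It is a low-cost improvement and does not correct an invalid analysis.

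**What to change.** In section 10.0:
- For PHE and for BMI or percent overweight, replace the t-test by a linear model of the T3 value on arm plus that outcome's own baseline, one value per family, with adolescents and caregivers analysed separately. Use that single covariate only.
- Define the baseline as a value taken before intervention content and supporter messages begin. For PHE this is the T0 survey, and the schedule table should be aligned with the text. For weight, use a first reading on the provided scale before W1 content, with screening BMI as the fallback.
- Include body fat only if such a pre-W1 reading exists.
- Keep the two-sample comparison for step count, physical activity, self-monitoring and other app measures without a true pre-intervention value.

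The analysis cost is one degree of freedom, and an interval up to about 5% wider if the correlation turns out below about 0.3. The data are already planned, apart from making sure that the first scale reading falls before W1.

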Aim 1: Feasibility Testing. Evaluate the DWN-FIT intervention (delivered by 2 CHWs) with 16 families (AAAO and caregiver, overweight or obese) undergoing treatment for adolescent obesity to determine the degree to which the DWN mobile app promotes the client's engagement in healthy behaviors, increased access to treatment for rural AA families, and improved treatment retention compared to the baseline (27% - 55% attrition). Additionally, we will determine the degree to which SS, as an additional element of DWN-FIT, enhances engagement and retention of families in the treatment.

Expected Outcome: We anticipate that healthy behaviors (increased step count, PA, nutrition SM, etc.) will be positively correlated with increased measures of engagement. Continuous engagement, we hypothesize, is highly linked to improved health outcomes, such as weight loss, which should also be reflected in measures of adherence. We also expect that SS will have a positive effect on each healthy measure, serving to increase the average step count, PA participation, and SM when compared to the non-SS condition.

Aim 2: User Centered Evaluations. Conduct a needs analysis before the intervention, a usability evaluation during the intervention and participant focus groups after the intervention to determine if the DWN app met their needs related to accessing (participants), delivering (CHWs), and providing support during the treatment.

Expected Outcome: We expect that the responses from the participants' surveys and the resulting themes will indicate that the DWN app met the participants' goals and needs related to accessing, delivering, and providing support during the treatment and was usable, efficient and effective.

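### Eleven measures are called primary and the arms are compared at 0.05 on an open list with no lead measure; the chance of at least one false positive is up to 43%, against the nominal 5%

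*Protocol*

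**What the plan says.** Section 9.0 (Aim 1, Methods) judges feasibility on the "development of healthy behaviors (primary outcomes" in its wording) and lists them as "step count, PA and PA video views, frequency and consistency of nutrition SM, messaging read and response rates", then "frequency and consistency of CBST education participation, telehealth session attendance, and CM rewards". They are collected often: "Primary outcomes will be measured after each session (weekly) through the data recorded by the DWN app". On the arms it says: "We will also determine the effect of semi-automated SS on each of the measures by comparing outcomes from each treatment group".

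The Data Analysis Strategy in Section 10.0 supplies the test: an "independent two-sample t-test ($\alpha = 0.05$) to determine statistical differences", applied to an open list ("to determine statistical differences between measures such as step count, PA, SM, etc"). Section 1.0 gives the expectation: "We also expect that SS will have a positive effect on each healthy measure".

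The assessment table in Section 9.0 is organised differently. It puts percent body fat under the primary outcome heading and physical activity and dietary self-monitoring under the secondary one. Percent body fat is in neither the primary nor the secondary list of the Aim 1 Methods text, where the secondary outcomes are percent overweight and BMI.

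**The concern.** A set of measures, all with primary status, is compared between arms at 0.05 each. Nothing says which of them carries the SS question, and the list in Section 10.0 can grow or shrink after the data are seen. The 0.05 is then the error rate of one comparison. It is not the error rate of a statement that SS improved a primary outcome.

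Sections 1.0 and 2.0 say that successful results will supply the evidence for a larger randomised trial, so an SS result labelled primary could shape that trial. With 8 families per arm, a difference must be large to reach significance at all (see the working), so a chance finding would also look like a strong effect.

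**Working it through.** The protocol gives no familywise error rate, power or sample-size derivation, so there is no figure of its own to reproduce beyond the per-test 0.05.

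**Inputs from the protocol**
- Per-test alpha 0.05, independent two-sample t-test (Section 10.0). Two-sided is assumed, as the side is not stated.
- 16 families randomised (Section 9.0), 8 of them to SS (Section 5.0), hence 8 v 8.
- Primary measures (Section 9.0): steps 1; activity and activity videos 2; nutrition self-monitoring 2; messaging 2; skills-training education 2; attendance 1; contingency rewards 1. Total 1+2+2+2+2+1+1 = 11 measures in 7 groups.

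**Inputs assumed**
- A common correlation between measures of 0 to 0.9. The protocol gives none, but positive correlation is expected: in Section 3.0 the rewards are paid for meeting the step, self-monitoring, education and activity goals.
- For the 22-test case only: adolescents and caregivers tested separately on all 11 measures (11 × 2 = 22), with an adolescent-caregiver correlation of 0 to 0.5.

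**Independent tests**, chance of at least one false positive = 1 − 0.95^k:
- k = 7: 1 − 0.698 = 30%
- k = 11: 1 − 0.569 = 43%
- k = 22: 1 − 0.324 = 68%
- Passing 50% needs k > ln 0.5 / ln 0.95 = 13.5, so at least 14 tests.

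**Correlated tests**, by simulation of null two-sided t-tests, 8 v 8, 40,000 runs per setting; false positives in either direction:

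| Tests | 0.3 | 0.5 | 0.7 | 0.9 |
|---|---|---|---|---|
| 7 | 28% | 24% | 19% | 12% |
| 11 | 38% | 31% | 23% | 13% |
| 22 | 59–62% | 51–53% | 40–42% | 24–26% |

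**False positives favouring SS only.** For 11 tests: 24% if independent, 16% at correlation 0.5. For 22 tests: 42% if fully independent, 26–29% at correlation 0.5.

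**Size needed for significance at 8 v 8.** The critical t on 14 degrees of freedom is 2.145, so the observed difference must exceed 2.145 × √(2/8) = 1.07 SD. The true difference detectable with 80% power is 1.51 SD at 0.05, and 2.15 SD at 0.05/11 = 0.0045.

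**The case against.** The strongest reply is that this is a 16-family feasibility study, that handling of multiple tests is commonly left to an analysis plan, and that the protocol never says one significant measure would count as success. Its stated expectation is an effect on every measure, and a claim that required all of them to be significant would need no adjustment.

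Much of this stands. The absence of an adjustment method is not the point, since a statistical analysis plan that is not shown could supply one. Strict familywise control would suit the study badly: at 0.05/11 only a difference of about 2.15 SD is detectable with 80% power. The protocol's success language also concerns the digital intervention as a whole more than SS.

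What remains is what the protocol itself fixes: eleven primaries, a stated alpha and an open list. The feasibility label does not cover the tests. Section 9.0 applies the term preliminary data to the secondary outcomes and the engagement survey, and speaks of exploring only for the link between SS and adherence. Which outcome is primary is a matter for the protocol, and here its text and table disagree.

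A reader might go further and infer that a chance SS effect is likely. The figures do not support that. With 11 tests the chance never exceeds 43%. A false result in favour of SS stays below 50% in every setting run. A reader might also infer that adolescents and caregivers are tested separately, because data come from both. The protocol does not say whether they are tested separately, pooled or per family, and a shared telehealth session may give only one attendance value per family.

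**Conclusion.** The point holds in a limited form. As written, the plan makes eleven measures primary and compares the arms at 0.05 on a list that is not closed, with no lead measure and no exploratory label, while its own table names a different primary outcome. If SS has no effect, the chance of at least one false positive in either direction is at most 43% for 11 two-sided tests, and about 38% down to 13% for assumed correlations of 0.3 to 0.9. Counting the seven groups as one test each gives 30% if independent and 12% at correlation 0.9. Every case is more than twice the nominal 5%.

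The 68% figure applies only under separate testing of both family members with all tests independent, and should be quoted only with that condition. All figures assume one test per measure. The protocol does not say how the weekly values are summarised, and testing by week or time point would raise them.

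**What to change.** 1. In Section 9.0, reconcile the Aim 1 Methods text with the assessment table on which outcome is primary. This comes first, because choosing a lead measure does not by itself settle the conflict.
2. Name one lead measure with its summary and unit, for example the adolescent's mean daily step count over weeks 1 to 12, one value per household. Make it the only between-arm test, at two-sided 0.05.
3. In Section 10.0, replace the open list with a closed one. Report all other measures as arm differences with 95% confidence intervals and no significance claim.

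A Bonferroni or Holm correction across the list is not advised with 8 families per arm, for the power reason given above.

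The cost is a few sentences in Sections 9.0 and 10.0 and a correction to the table, with no extra participants or data. The downside is fewer nominally significant results to quote.

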11.0 Provisions to Monitor the Data to Ensure the Safety of Subjects

The PI will ensure that the trial is conducted according to the approved IRB protocol and will also be responsible for carrying out the data and safety monitoring plan. Basic demographic data about the participants will be collected to ensure they meet the inclusion/exclusion criteria of the study. Data elements collected on paper records will be de-identified to protect study participants' names and identifiers and will be stored in a secure locked cabinet at the RA's MUSC office. The audio recordings from the family sessions and focus groups along with the mobile app chat messages will be downloaded and stored on Box, a HIPAA compliant and MUSC approved protected Cloud Storage System. There is no risk involved in storing the paper records and audio recordings. There is a greater risk storing the data digitally, but we have taken the following steps described in the next paragraph to ensure privacy and security.

After enrolling in the study and finishing the consent process the adolescent, caregiver and support person will be granted access to DWN by a Community Health Worker (CHW). DWN platform is secure and private. Individuals can only use the DWN app through a patient identification (ID) number, a random 9-digit code assigned to them by their CHW. This ID is emailed to the patient along with a link to download the app from the app store. The patient uses the code to register when using the app for the first time. During registration the patient also creates a 6-digit pin, which they use to open the DWN mobile app in order to sign in. This 6-digit pin means the app is password protected. The information transmitted from the app to the cloud is encrypted. The data is also encrypted on the phone and in the cloud database. We have also taken extra precautions in protecting the privacy of the patient by choosing not to store any identifiable information in the same database as health data collected (health and usability assessment responses, wearable data from physical activity, and body fat), meaning the health data in the cloud are associated only with the random patient ID. The patients' names and emails are stored in a file location accessible only by the healthcare provider and senior personnel conducting the study.

Institutional Review Board

Adverse and Serious Adverse Events. Any adverse events (AEs) or serious adverse events (SAEs) that are observed and/or reported will be immediately reported to PI [name]. An adverse event is any reaction, side effect or untoward event that occurs during the course of the study. Adverse events are categorized as serious (see below) or non-serious, as related or not related to the study intervention, and as expected or unexpected. For the purpose of the present trial, clinically insignificant events will be excluded from any type of AE documentation. These include colds, flu, cuts, scrapes, coughs, headaches, stomach complaints, general fatigue and mild symptoms. Behavioral AEs that will be tracked in this trial include injury due to physical activity or increases in adolescent behavior problems or family conflict. Serious adverse events (SAEs) are defined as deaths, life-threatening events, permanently or substantially disabling events, congenital anomalies, events

requiring an initial hospitalization or prolonging a current hospitalization, or events that require intervention to prevent permanent impairment or damage. Participants will be screened for AEs and SAEs at each study data collection visit except baseline. AEs and SAEs will be formally elicited at each scheduled data collection point, using an AE Worksheet that will include the expected AEs discussed above and general probes for other physical or behavioral difficulties since the last study contact. AEs that are reported to research staff at times other than those detailed above (e.g. during a phone call to schedule data collection, while working with the computer) will also be recorded and reported as described below. All clinically significant AEs will be categorized as an SAE or non-SAE, as expected or unexpected, and as likely or unlikely to be related to the study treatment by the Co-I or his designate. The Co-I will review all AE reports for concurrence regarding relatedness to the intervention, seriousness, and appropriate resolution. The Co-I or his designate will track all SAEs until resolution has been achieved. All SAEs and AEs will be entered into the study database so that they may be reported to the data and safety monitor. If an SAE is determined to be related to the intervention, then it will be reported to the Data and Safety Monitoring Officer in real time (within 48 hours of occurrence or identification by study personnel).

DSMP Administration

The PI will be responsible for monitoring the safety of this trial, executing the DSMP, and complying with the reporting requirements. Data are randomly inspected weekly and inspected thoroughly on a quarterly basis. All DSMP reports to NIMHD will include a brief description of the trial, baseline sociodemographic characteristics, retention and disposition of study participants, Quality Assurance issues, regulatory issues, AEs and SAEs, and efficacy, as well as any actions or changes with respect to the protocol.

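### Minor events possibly caused by the workouts or diet changes can be dropped before relatedness is judged, and the exclusion overlaps unresolved with the tracking of exercise injury

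*Protocol*

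**What the plan says.** All the rules stand in one paragraph of Protocol section 11.0, on adverse and serious adverse events.

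- **Definition:** "An adverse event is any reaction, side effect or untoward event that occurs during the course of the study". It sets no severity threshold.
- **Reporting to the PI:** "Any adverse events (AEs) or serious adverse events (SAEs) that are observed and/or reported will be immediately reported to PI".
- **Exclusion:** for this trial, "clinically insignificant events will be excluded from any type of AE documentation". The examples follow: "These include colds, flu, cuts, scrapes, coughs, headaches, stomach complaints, general fatigue and mild symptoms".
- **Tracked events:** "Behavioral AEs that will be tracked in this trial include injury due to physical activity or increases in adolescent behavior problems or family conflict". Again there is no severity threshold.
- **Relatedness:** the general statement covers AEs as a whole: "Adverse events are categorized as serious (see below) or non-serious, as related or not related to the study intervention, and as expected or unexpected". The operative sentence later in the paragraph is narrower: "All clinically significant AEs will be categorized as an SAE or non-SAE, as expected or unexpected, and as likely or unlikely to be related".
- **Database:** "All SAEs and AEs will be entered into the study database so that they may be reported to the data and safety monitor".

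The same paragraph provides for an AE Worksheet at each scheduled data collection point. It lists the expected AEs and adds open questions about other physical or behavioral problems. Under DSMP Administration, section 11.0 makes AEs and SAEs part of the reports to NIMHD.

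**The concern.** Screening out background illness is a reasonable aim in a small behavioral study. The difficulty is that the screen works on how minor an event is and takes no account of what may have caused it. The intervention in section 3.0 has adolescents and overweight or obese caregivers do unsupervised interval and resistance workouts. It also teaches nutrition and the management of hunger and cravings, and it pays adolescents a bonus for sustained weight reduction. Tiredness, headache, stomach upset and small injuries are plausible effects of such a programme, and they are on the excluded list.

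Section 12.0 names only embarrassment and distress from disclosure as risks, so physical effects of the programme would have to show up in the AE record. If that record is filtered before cause is considered, a low count of related minor AEs cannot be read as good tolerability. Two staff members could also record the same scrape from a workout differently, each following a sentence of the protocol.

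**Working it through.** No figure in the protocol bears on this point and no arithmetic applies. The check sets the sentences of the AE paragraph against each other.

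**Step 1: order of the filter and the judgement.** Events are elicited on the worksheet. Clinically insignificant ones are then left undocumented. What remains, the clinically significant AEs, is categorized for seriousness, expectedness and relatedness, and the Co-I reviews the reports. The exclusion therefore comes before relatedness. It contains no exception for a suspected link with the intervention, and the paragraph does not say who decides that an event is insignificant.

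**Step 2: the rules applied to four kinds of event.**

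| Event | Exclusion | Injury tracking | Relatedness judged? |
|---|---|---|---|
| A cold with no link to the study | Excluded | Does not apply | No, and little is lost |
| Minor headache, stomach upset or tiredness after a workout or diet change | Excluded | Does not apply, as these are not injuries | No |
| Cut, scrape or mild symptom from a workout | Excluded | Tracked where it counts as an injury | Unclear, as the text points both ways |
| Clinically significant workout injury | Not excluded | Tracked | Yes |

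**Step 3: where the fault lies.** The second row is a loss of information: the event may be related, but no one is asked to judge it. The third row is an unresolved overlap: the same event is barred from documentation by one sentence and to be tracked under the next. The sentences sending any AE to the PI and all AEs to the database carry no qualification either, so they do not settle the matter. The first and fourth rows raise no difficulty.

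**Step 4: reach of the list.** Eight of its nine entries are recognizable minor complaints. The ninth, mild symptoms, is open-ended and works as a severity cut-off for anything not named.

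**Step 5: effect on reports.** AEs go into the DSMP reports. Under the exclusion as written, the number of minor related AEs reported can only be too low, never too high. The protocol gives no expected rate for such events, so the shortfall cannot be sized.

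**The case against.** The strongest reply is that the exclusion is a deliberate choice of scope. It is announced as applying to this trial, and the later sentence on categorization uses the same threshold of clinical significance, so the two fit together. The listed complaints are examples of insignificant events, and a severe or lasting headache could still be treated as significant. Exercise injury is named as tracked, with no severity floor, and the worksheet asks about expected AEs and about other difficulties. If the specific rule prevails over the general one, a scrape from a workout is recorded. The study has 16 families and no safety endpoint in its aims or in the analysis strategy of section 10.0, so no trial result turns on minor AEs.

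Much of this stands, and it rules out several stronger readings that a reader might draw:

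- **That the exclusion simply contradicts the AE definition.** It is an announced narrowing. The tension is with the unqualified reporting and database sentences and with the injury sentence.
- **That a mild workout injury never reaches the Co-I.** It may or may not, depending on which sentence staff follow.
- **That excluding headache, stomach complaints or tiredness conflicts with injury tracking.** These are not injuries. For them the only fault is loss before relatedness is judged.
- **That a number of missed events can be stated.** Multiplying an assumed rate by the 32 adolescents and caregivers only returns the assumption.
- **That the future randomized trial will inherit a false safety profile.** The protocol says this study should support that trial, but not that the trial's safety plan will rest on these counts.

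The reply does not remove the order of filter and judgement, and it does not supply the missing sentence saying which rule governs a minor workout injury. That the specific rule prevails is a sensible inference, but the protocol does not state it.

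**Conclusion.** The point holds in a limited form. If the protocol is followed as written, minor events plausibly caused by the workouts or diet changes can go undocumented without any judgement of cause. Cuts, scrapes and mild symptoms from workouts are subject to two incompatible instructions. SAEs, clinically significant AEs and clinically significant injuries are unaffected.

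The consequence is an understated count of minor related AEs in the DSMP reports and possible inconsistency between staff. The direction is clear and the size unknown. The conclusion rests on reading the listed complaints as normally insignificant and on the workouts and diet changes being able to cause some of them. Both seem safe, but neither can be quantified from the protocol. This should be corrected, though it threatens none of the trial's stated aims. It is not a matter left to a statistical analysis plan, because the protocol itself sets the documentation rule.

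**What to change.** Reconcile the exclusion, the injury sentence and the database sentence in section 11.0 by adding that the exclusion does not apply to:

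1. any injury from physical activity, however minor;
2. any listed event that began during or after a study workout, with the protocol stating how long after counts;
3. any listed event that the participant or staff connect with the workouts, diet changes or weight loss.

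Record these on the existing AE Worksheet and send them to the Co-I for the relatedness judgement. The timing criterion matters because a rule based on attribution alone would again filter on cause before the Co-I sees the event. The exclusion can stay for background illness that meets none of these conditions. State who decides that an event is clinically insignificant.

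The change concerns documentation only. It costs a few more worksheet entries and a slightly higher reported AE count, some of which will be events that the Co-I judges unrelated.
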